3.4 Phase II

Enrollment in the Phase II portion of the study (dose expansion) will begin once the MTD has been determined. After Cycle 1, subjects with progressive disease will be removed from study. Others will continue to receive 28-day cycles of ciprofloxacin and etoposide at the same dose level until completion of Cycle 2, disease progression, unacceptable toxicity, consent

withdrawal, PI decision to discontinue treatment, or termination of the study. No subject will receive more than 2 cycles of therapy.

3.5 Study Duration

The subject recruitment period is approximately 48 months. The study duration encompasses the following:

- Screening period of up to 21 days;
- Treatment with ciprofloxacin and etoposide until the endpoints defined under Section 3.4 are met; and
- Day 28 follow-up after the last cycle of therapy.
- No subject will receive more than 2 cycles of therapy from Day 1 of Cycle 1.

3. SELECTION OF SUBJECTS

3.1 Number of Subjects

The number of subjects enrolled in Phase Ib to be 8-24 depending upon toxicity, after accounting for a 25% drop-out rate during the first 28-day cycle. In Phase II, up to 44 subjects with relapsed and/or refractory AML will be enrolled. Justification for sample size in phase II is provided in [Section 11.1](#). Subjects in this study can be of any race, gender and ethnic group.

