Safety Assessments:	
Subjects will be evaluated weekly during and for at least 28 days following the last cycle of chemotherapy. Assessments will include (See Table 1):
 
 • Interval history, review of systems, medications, new allergies, and physical examination with vital sign measurements; • Weekly laboratory assessments, including a CBC with differential and CMP; and • Toxicity assessment per the NIH Common Toxicity Criteria Adverse Event (CTCAE) version 4.
Efficacy Assessments:	
Efficacy parameters used to assess response include hemoglobin, ANC, platelet count, circulating blasts, and bone marrow aspirate and/or biopsy.

Sample Size Estimation	
In prior clinical trials of oral etoposide in resistant AML the CR rate has been approximately 20%. It is expect that the combination of etoposide with ciprofloxacin will improve CR to 40%. In order to detect this difference with type I error rate of 0.10 and power of 80%, when the true response rate is 40%, a minimum of 24 evaluable subjects will be treated in Phase II based on the Simon’s two-stage MiniMax design. Accounting for 15-20% drop out rate, a total of 30 subjects will need to be recruited to this phase.

Table 1. Study Events Schedule

Assessment	Screen (≤ 21 days prior to Day 1)	Cycle 1					Cycle 2		End of Treat- ment ¹² ± 7days	Long- Term Follow Up ¹³
		Day 1	Day 8±2	Day 15±2	Day 22±2	Day 28±2	Days 1, 8, 15, 22±2	Day 28±2		
Signed Informed Consent	X									
Demographics	X									
Medical /Treatment History	X									
Medication History ¹	X	X	X	X	X	X	X	X	X	
Interval History/Physical Examination	X	X	X	X	X	X	X	X	X	
Toxicity Assessment		X	X	X	X	X	X	X	X	
Review of Systems		X	X	X	X	X	X	X	X	
Weight	X	X	X	X	X	X	X	X	X	
ECOG Performance Status	X	X	X	X	X	X	X	X	X	
12-lead electrocardiogram (ECG) ²	X		X			X			X	
Vital Signs ³	X	X	X	X	X	X	X	X	X	
Hematology Laboratory Evaluations ⁴	X	X	X	X	X	X	X	X	X	
Blood Chemistry Laboratory Evaluations ⁵	X	X	X	X	X	X	X	X	X	
Serum Pregnancy Test (females) ⁶	X					X		X	X	
Administer Ciprofloxacin ⁷		X	X				X			
Administer Etoposide ⁸			X				X			
Bone Marrow Aspirate and/or Biopsy ⁹	X					X		X	X	
Adverse Events Assessments ¹¹	X	X	X	X	X	X ¹³	X	X	X	
Survival Assessment										X

¹ Document all medications taken during the two (2) weeks prior to screening and throughout and for 28 days after last treatment.

² Includes: rhythm, rate, and PR, QRS, and QTc intervals.

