9.2 Replacement of Subjects

Subjects who are withdrawn prior to C1D1 for any reason will be replaced.

Phase Ib - Subjects who withdraw or are withdrawn from study prior to C1 Day 28 without a DLT will be replaced by another subject.

Phase II - Subjects who withdraw or are withdrawn prior to receiving one full cycle of therapy will be replaced by another subject.

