11.1 Determinations of Sample Size

An estimate of 8-24 patients are to be enrolled to Phase Ib portion of the study accounting for a 25% drop-out rate. Precise sample size cannot be defined, as it is dependent on the observed toxicity rate in this phase.

Subjects will be enrolled in the Phase II portion of the study once the MTD has been determined. The primary intention is to determine the complete response rate (CR + CR_i, see [Appendix A](#)) of ciprofloxacin and etoposide given at the MTD to subjects with resistant AML, which is achieved at the end of any treating cycle. The CR rate for AML subjects receiving etoposide alone is approximately 20% (the null hypothesis). We expect that the combination of ciprofloxacin and etoposide will improve the CR rate to 40%. In order to detect this difference with a type I error rate of 0.10 and power of 80%, when the true response rate is 40%, a minimum of 24 subjects who are evaluable for response will need to be accrued, based on the Simon's two-stage Minimax design. Specifically, in the first stage, we will enroll 14 evaluable subjects to this phase. The accrual will be temporarily suspended once the 14th evaluable subject is enrolled, pending response evaluation. If 2 or fewer respond, in these 14 subjects, the study will be stopped. Otherwise, continue to accrue additional 10 evaluable subjects (for a total of 24 evaluable subjects). The null hypothesis of 20% CR will be rejected if 8 or more CRs are observed in 24 subjects. Assuming 20% drop out rate, the total number of subjects to be enrolled to the Phase II portion is 30

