11.2.3 Efficacy Evaluable Population

The efficacy population will include all subjects who receive at least 1 cycle of ciprofloxacin and etoposide and had at least one post-dose efficacy assessment.

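### Section 3.1 (Number of Subjects) allows up to 44 Phase II subjects, but the section it cites derives 30 and nothing derives 44; no CR rate in all treated subjects is planned.

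*Combined protocol and SAP*

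**What the plan says.** **Enrolment.** Section 3.1 (Number of Subjects, under Selection of Subjects) says: "In Phase II, up to 44 subjects with relapsed and/or refractory AML will be enrolled". The next sentence begins "Justification for sample size in phase II is provided in" and points to Section 11.1.

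Section 11.1 sets out a Simon two-stage minimax design and says that "a minimum of 24 subjects who are evaluable for response will need to be accrued". It ends: "Assuming 20% drop out rate, the total number of subjects to be enrolled to the Phase II portion is 30". The synopsis agrees: "Accounting for 15-20% drop out rate, a total of 30 subjects will need to be recruited to this phase".

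**Replacement.** Section 9.2 covers both phases with "Subjects who are withdrawn prior to C1D1 for any reason will be replaced". For Phase II it adds: "Subjects who withdraw or are withdrawn prior to receiving one full cycle of therapy will be replaced by another subject". It sets no limit on the number of replacements.

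**Analysis.** Section 11.2.3 defines the efficacy population as "all subjects who receive at least 1 cycle of ciprofloxacin and etoposide and had at least one post-dose efficacy assessment". Section 11.3.2 plans frequencies with 95% confidence intervals and names no other denominator. The safety population in Section 11.2.1 requires a dose of each drug and is used for safety summaries.

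**The concern.** The cross-reference fails: a reader who follows Section 3.1 to Section 11.1 finds a different total and no route to the one in Section 3.1. The documents therefore do not settle how many Phase II subjects may be enrolled, or whether 30 is a plan, a limit or both.

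The second matter is a separate omission that the enrolment sentence does not itself show. A Phase II subject who takes study drug and then leaves before one cycle is replaced and drops out of the CR denominator. Such losses may well be related to outcome: the life-expectancy criterion is only 4 weeks or more, and the first post-baseline marrow is at Day 28. If those lost early are mainly non-responders, the evaluable-only CR rate is too favourable, and no planned table would show by how much. The safety population does not fully fill the gap. Etoposide starts on Day 2, so someone lost after Day 1 belongs to neither population.

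**Working it through.** **Inputs (Section 11.1 unless noted).** Null CR rate 0.20; alternative 0.40; type I error 0.10; power 0.80. Stage 1 has 14 evaluable subjects, stopping at 2 or fewer responses; the total is 24 evaluable, rejecting at 8 or more. Drop-out is 20% (synopsis: 15-20%).

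**Step 1: reproduce the design.** P(reject | p) = sum over x = 3 to 14 of P(X1 = x) × P(X2 ≥ 8 − x), with X1 ~ Bin(14, p) and X2 ~ Bin(10, p).
- p = 0.20: 0.087.
- p = 0.40: 0.802.
- Probability of stopping at stage 1: P(X1 ≤ 2) = 0.448 at p = 0.20 and 0.040 at p = 0.40.

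An exhaustive search over two-stage designs with these inputs returns the same minimax design.

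**Step 2: reproduce 30.** Enrolled = evaluable / (1 − loss).
- 24 / 0.80 = 30.
- 24 / 0.85 = 28.2, so 29.

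The 30 in Section 11.1 and the synopsis is confirmed.

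**Step 3: try to reach 44.**
- Excess: 44 − 30 = 14, and 14 / 30 = 47%.
- Loss needed: 1 − 24/44 = 45.5%.
- Other inputs can give 44. Examples are type I error 0.05 (minimax n = 33) with 25% loss, 33 / 0.75 = 44; or power 0.90 (optimal n = 37) with 15% loss, 37 / 0.85 = 43.5, so 44. None of these sets of inputs is stated for Phase II.

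**Step 4: what a replacement margin would look like (illustration).** Assume independent losses, full accrual and no further replacement beyond N. P(fewer than 24 evaluable) = P(Bin(N, 1 − loss) ≤ 23).

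| N | 20% loss | 15% loss |
|---|---|---|
| 30 | 0.39 | 0.15 |
| 35 | 0.034 | 0.004 |
| 44 | 0.00003 | below 0.00001 |

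At 20% loss, 35 enrolled gives at least 24 evaluable with probability 0.97.

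**Step 5: size of the possible selection effect.** Assume a true CR rate of 0.20 in all treated subjects. Let d be the share of dosed subjects lost, and f the response rate of those lost relative to the overall rate. The evaluable CR rate is then 0.20 × (1 − d × f) / (1 − d). Put this rate into the formula of Step 1:

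| d | f = 1 | f = 0.5 | f = 0 |
|---|---|---|---|
| 5% | 0.087 | 0.099 | 0.111 |
| 10% | 0.087 | 0.113 | 0.142 |
| 15% | 0.087 | 0.129 | 0.180 |
| 20% | 0.087 | 0.149 | 0.230 |

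Example: d = 20%, f = 0 gives 0.20 / 0.80 = 0.25 and P(reject) = 0.230.

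**Step 6: what the supportive rate would show.** At the rejection boundary with 24 evaluable, 8/24 = 33.3% (exact 95% CI 15.6% to 55.3%). If all 30 were dosed and the other 6 count as non-responders, 8/30 = 26.7% (12.3% to 45.9%).

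**The case against.** The best defence is the phrase setting an upper limit. Section 3.1 can be read as a ceiling, Section 11.1 gives 30 under an assumed 20% drop-out and calls 24 a minimum, and Section 9.2 replaces early losses without a cap. A planned 30 and a ceiling of 44 can coexist. That much stands, so the two figures need not be rival targets. What the defence cannot supply is a source: no text calls 44 a replacement ceiling, and the section cited for it does not mention it. Nor is it a whole-study total: the sentence is about Phase II, and 30 plus the 8-24 of Phase Ib is 38-54.

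Four stronger readings might tempt a reader; the documents support none of them.

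- **The committee's accrual report has two competing targets.** Section 10 lists target and actual accrual as report items. It attaches no action to a mismatch, and the ceiling reading removes the conflict.
- **The plan expects 45% loss, or 30 is too few.** The 45% arises only if all 44 are enrolled and exactly 24 are evaluable, which nothing plans. The 0.39 shortfall requires that the trial passes stage 1 and that enrolment stops at 30, which the replacement rule does not require.
- **The type I error is inflated.** The values in Step 5 rest on assumed losses and response ratios. The plan gives neither the dosed share of the drop-out allowance (some replaced subjects never start treatment) nor the denominator behind the 20% null.
- **The Cycle 1 Day 28 visit text defines a completed cycle for evaluability.** Sections 9.2, 4.1 and 11.2.3 do word the cycle requirement differently. But the Day 28 statement in Section 6.2 concerns visit timing, and ciprofloxacin, the later of the two drugs to finish, ends on Day 10. Using it as the definition could exclude a fully dosed subject who died before Day 28 and so worsen the selection.

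**Conclusion.** The enrolment figure in Section 3.1 is unsupported as written: 44 against a derived 30, a gap of 14 subjects (47%), with the cited justification giving the lower number. This rests on the text and on 24 / 0.80 alone and is certain. Whether 44 is an intended ceiling or a mistake cannot be determined from the documents. The test is not affected: the decision depends on 14 and then 24 evaluable subjects, with type I error 0.087 and power 0.802.

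The absence of an all-treated CR rate is also certain; its effect is not. If the true all-treated CR rate is 20%, the chance of rejecting stays 0.087 when loss is unrelated to response, and is 0.111 to 0.230 when 5-20% of dosed subjects are lost and none respond. These figures show why a supportive rate is worth having. They are not error rates of this trial.

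**What to change.** 1. In Section 3.1, state 30 as the planned Phase II enrolment, in agreement with Section 11.1 and the synopsis. If replacements may take enrolment higher, give a separate maximum with its derivation in Section 11.1 and repeat that figure in Section 3.1. A maximum of 35 on the basis of Step 4 is one illustration; the sponsor should choose its own criterion.
2. Keep the 14/24 evaluable test as the only decision rule. Add to Section 11.3.2 a supportive CR rate with an exact 95% CI in all Phase II subjects who took at least one dose of either study drug, counting those without a response assessment as non-responders.
3. Reconcile the cycle requirement across Sections 9.2, 4.1 and 11.2.3, without making survival to Cycle 1 Day 28 a condition of being evaluable.

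The cost is text edits and one extra table. The design, its type I error and its power do not change. The supportive rate may look less favourable than the evaluable one, and a maximum above 30 means planning for those extra subjects (5 more if it is 35).

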3.2 Inclusion Criteria

- A. Age \geq 18 years.
- B. Diagnosis of AML confirmed by review of bone marrow pathology at the University of Florida.
- C. Patients with relapsed and or refractory AML
 - who failed to achieve CR or CRi after at least one cycle of induction chemotherapy and not suitable for second cycle of standard intensive chemotherapy,
 - who have progressed after 1 cycle of HMA or intolerant to HMA therapy and not suitable for standard induction chemotherapy regimens.
 - who have relapsed after any duration of response,
- D. Per the treating physician, the subject must have a life expectancy of \geq 4 weeks.
- E. Subject performance status must be Eastern Cooperative Oncology Group (ECOG) 0, 1, or 2 (see [Appendix B](#)).
- F. Subject must have total bilirubin \leq 2 mg/dL and AST and ALT \leq 2.5 times the upper limit of normal.
- G. Subject must have serum creatinine $<$ 2 mg/dL.
- H. Females of child-bearing potential (*i.e.*, women who are pre-menopausal or not surgically sterile) may participate, provided they meet the following conditions:
 - Must agree to use physician-approved contraceptive methods throughout the study and for 6 months following the last dose of ciprofloxacin and/or etoposide. Adequate forms of contraception are abstinence, double-barrier methods (*e.g.*, condoms with spermicidal jelly or foam and diaphragm with spermicidal jelly or foam), oral, depot, or injectable contraceptives, intrauterine devices, and tubal ligation.

- Must have a negative serum pregnancy test within 7 days prior to beginning treatment on this study.
- I. Males with female partners of child-bearing potential must agree to use physician-approved contraceptive methods (*e.g.*, abstinence, condoms, vasectomy) throughout the study and should avoid conceiving children for 6 months following the last dose of ciprofloxacin and/or etoposide.
- J. Subjects must have provided written informed consent and be willing to comply with all study-related procedures.

3.3 Exclusion Criteria

Subjects with any of the following will not be eligible for study participation:

- A. History of allergic or significant adverse reaction (*e.g.*, anaphylaxis, prolonged QTc, or severe tendonitis) to ciprofloxacin or etoposide.
- B. Acute promyelocytic leukemia (APL) with t(15;17).
- C. Prolonged baseline QTc, defined as QTc interval > 470 msec in women and > 450 msec in men, or > 480 msec in subjects with a bundle branch block.
- D. Uncontrolled, clinically significant infection. Subjects with fever (temperature ≥ 38.3) thought to be related to leukemia are eligible assuming that blood cultures are negative during the 7 days prior to Cycle 1 Day 1 and there is no clinical evidence of active infection (*e.g.*, negative or stable radiographs and negative physical examination).
- E. Ongoing, symptomatic *Clostridium difficile* infection. Subjects who are asymptomatic with negative stool for *C. difficile* may participate.
- F. Pregnant and/or nursing.
- G. History of Myasthenia Gravis.
- H. Treatment with any anticancer therapy (standard or investigational) within 14 days prior to the first dose of ciprofloxacin or less than full recovery (\leq CTCAE grade 1) from the clinically significant toxic effects of that treatment. The use of hydroxyurea is allowed only during the first 14 days of Cycle 1.

4. STUDY TREATMENT

All subjects entering the screening phase will receive a unique subject number. This number will be used to identify the subject throughout the study. Subjects withdrawn from the study will retain their subject number.

4.1 Etoposide and Ciprofloxacin

Ciprofloxacin will be administered orally twice daily on Days 1 to 10 of each 28-day cycle. Whenever possible, doses should be taken at 0800 hours and 2000 hours. If for some reason the doses are not taken at these times, ciprofloxacin can be taken as late as 6 hours after the scheduled time. If > 6 hours elapses, that dose of ciprofloxacin will be held and not made up. The starting dose will be 750 mg (dose level 0) with escalation to a maximum of 1000 mg (dose level +1) or de-escalation to a minimum of 500 mg (dose level -1).

Etoposide at a fixed dose of 200 mg will be administered orally once daily on Days 2 to 8 of each 28-day cycle. Subjects will be instructed to take etoposide with their morning dose of ciprofloxacin at 0800 hours on an empty stomach. If for some reason the dose is not taken at this time, it may be taken as late as 6 hours after the scheduled time. If >6 hours elapses, that dose of etoposide will be held and not made up.

A medication diary will be given to all subjects and they will be instructed to record the actual times they take both etoposide and ciprofloxacin. Doses missed will be recorded as such. Subjects will be told to call within 12 hours of missing a dose. Subjects will be instructed to bring the diary and any unused medication with them to all study visits. Any unused medication will be disposed of per institutional standard practice.

Subjects in Cycle 1 of Phase Ib who miss any etoposide or ciprofloxacin doses will be considered evaluable only if a DLT occurs. Otherwise they will be removed from the study on Day 28 and replaced in the cohort in which they were treated. Subjects in Phase Ib beyond the first cycle and those in Phase II will be considered evaluable for response if they have received at least one cycle in accord with the protocol. For these subjects non-compliance with dosing will be dealt with at the discretion of the PI.

Standard administration instructions will be given to each subject for ciprofloxacin (*e.g.*, separating administration from dairy products, calcium-fortified juices, sucralfate, antacids, or other medications that contain aluminum, magnesium, calcium, iron, or zinc). Subjects will be advised not to consume grapefruit or grapefruit juice within 7 days prior to starting ciprofloxacin and until 7 days after completion of all doses of ciprofloxacin on study.

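### The Phase II counts of 14 and 24 rest on an evaluable set that Sections 4.1, 9.2 and 11.2.3 define differently, and treated early failures are replaced, so the 0.10 type I error is not guaranteed

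*Combined protocol and SAP*

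**What the plan says.** Section 11.1 gives a Simon two-stage Minimax design with a 20% null, a 40% target, type I error 0.10 and power 80%. Both stages are counted in evaluable subjects: "The accrual will be temporarily suspended once the 14th evaluable subject is enrolled, pending response evaluation". The trial stops at 2 or fewer responders in 14. At the end, "The null hypothesis of 20% CR will be rejected if 8 or more CRs are observed in 24 subjects". Section 11.1 does not say who is evaluable. Three other sections bear on it:

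- **Section 4.1** treats a Phase II subject as evaluable for response after at least one cycle given according to protocol. It then says: "For these subjects non-compliance with dosing will be dealt with at the discretion of the PI". No number of missed doses is tied to evaluability.
- **Section 9.2**: "Phase II - Subjects who withdraw or are withdrawn prior to receiving one full cycle of therapy will be replaced by another subject". No reason for leaving is excepted.
- **Section 11.2.3** defines the efficacy population as "all subjects who receive at least 1 cycle of ciprofloxacin and etoposide and had at least one post-dose efficacy assessment". Adherence is not mentioned.

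No section counts a treated but non-evaluable subject as a non-responder. Section 11.3.2 plans no response analysis in all treated subjects. The Synopsis allows for 15-20% drop-out and Section 11.1 for 20%; both arrive at 30 enrolled.

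**The concern.** The thresholds of 2/14 and 8/24 have their stated error rates only if membership of the counted set is unrelated to response. Section 9.2 does not ensure this. Toxicity, intercurrent illness and the physician's opinion are all grounds for ending treatment under Section 4.2, and eligibility requires a life expectancy of only 4 weeks or more against a 28-day cycle. Loss during Cycle 1 is foreseeable, and such subjects are unlikely to respond as often as those who complete the cycle. Replacing them takes treatment failures out of the denominator and raises the apparent CR rate. The stage 1 stop and the final test, which are the primary Phase II decisions, both use that denominator.

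**Working it through.** **1. The definitions side by side.** A cycle has 27 scheduled doses (20 of ciprofloxacin, 7 of etoposide).

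| Phase II subject | 4.1 | 9.2 | 11.2.3 |
|---|---|---|---|
| Misses a few doses, has the Day 28 marrow | Not determined | Not replaced | Counted, on a natural reading |
| Dies or is withdrawn for toxicity or deterioration before completing Cycle 1 | Not evaluable | Replaced | Not counted |
| Completes Cycle 1, no post-dose efficacy assessment | Evaluable | Not replaced | Not counted |
| Completes Cycle 1, progression found at Day 28 | Evaluable | Not replaced | Counted |

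The sections give different answers in the first and third rows. In the second they agree, but the effect is to drop a treatment failure.

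**2. The plan's own design.** With p the response rate among counted subjects,

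P(reject) = sum over x = 3 to 14 of Bin(x; 14, p) × P(X2 ≥ 8 − x), where X2 ~ Bin(10, p).

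- p = 0.20: P(reject) = 0.0874; probability of stopping at stage 1 = 0.448.
- p = 0.40: P(reject) = 0.802.
- An exhaustive Minimax search under the stated error rates returns the same design, and 24/(1 − 0.20) = 30.

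The design is correct for the set it assumes.

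**3. Effect of replacement.** Let the true rate among all treated subjects be 0.20 and let a share d of them be replaced.

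- If no replaced subject would respond: p = 0.20/(1 − d).
- If replaced subjects respond at half the rate of counted ones: p = 0.20/(1 − d/2).

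The formula in step 2 is then evaluated at that p. The values of 15% and 20% are the plan's drop-out figures. Treating all of that drop-out as replaced treated subjects is an assumption, as are the response rates assigned to them.

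| Replaced subjects | d | p among counted | P(reject) |
|---|---|---|---|
| Replacement unrelated to response | any | 0.200 | 0.087 |
| Half the response rate | 15% | 0.20/0.925 = 0.216 | 0.125 |
| Half the response rate | 20% | 0.20/0.90 = 0.222 | 0.142 |
| All non-responders | 2.8% | 0.206 | 0.100 |
| All non-responders | 5% | 0.20/0.95 = 0.211 | 0.111 |
| All non-responders | 10% | 0.20/0.90 = 0.222 | 0.142 |
| All non-responders | 15% | 0.20/0.85 = 0.235 | 0.180 |
| All non-responders | 20% | 0.20/0.80 = 0.250 | 0.230 |

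The nominal 0.10 is passed once about 2.8% of treated subjects are replaced non-responders, which is 0.028 × 30 = 0.84, or about one subject in 30. At d = 20% with no responders among those replaced, the chance of stopping an inactive regimen at stage 1 falls from 0.448 to 0.281.

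**4. Counting every treated subject.** With 2/14 and 8/24 unchanged, type I error is 0.087 whatever the drop-out. Power depends on what the 40% describes:

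- All treated subjects: 0.802.
- Completers only, 15% drop-out: p = 0.40 × 0.85 = 0.34, power 0.597.
- Completers only, 20% drop-out: p = 0.40 × 0.80 = 0.32, power 0.514.

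**The case against.** Four points can be made for the plan.

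**Investigator discretion.** A reader might infer from Section 4.1 that the investigator can set aside non-responders with missed doses after seeing the Day 28 marrow. The text does not say so. It gives the investigator the handling of non-compliance, not expressly the decision on evaluability, and it does not say when that handling happens. Dosing ends on Day 10, subjects are told to call within 12 hours of a missed dose, and diaries come to every visit, so non-compliance can be known well before the marrow. Section 4.1 also provides for late doses to be omitted, so a cycle with a few missed doses may still be according to protocol. What stands is the missing threshold. Whether it could lead to selective exclusion is unclear, and no figure should be attached to it.

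**Progression.** A reader might infer that progressing subjects are generally replaced. Most would not be. Progression is defined on marrow blasts, the on-study marrow is at Day 28, and Section 3.4 removes Phase II progressors after Cycle 1. Those subjects count. The gap concerns loss during Cycle 1.

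**Timing of drop-out.** The 15-20% is not dated. It may include subjects lost before Cycle 1 Day 1, whose replacement does no harm. This stands, and it is why the results are given as a range.

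**The 20% benchmark.** Its denominator is not given. If it is a rate among evaluable subjects defined in the same way, the comparison is like with like and the inflation does not follow. This also stands, but the plan would have to say so.

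**Conclusion.** The point holds as a defect in the definition of the primary denominator. Section 11.1 relies on a term that three sections specify differently, and Section 9.2 followed as written can remove treatment failures from the count. The type I error of 0.10 is no longer guaranteed. It would go too far to say that it is lost: the documents fix neither how many treated subjects will be replaced nor how they would have responded.

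Given a true all-treated rate of 20%, the false-positive rate runs from 0.087 (replacement unrelated to response) through 0.125-0.142 (half the response rate, 15-20% replaced) to 0.18-0.23 (no responders among the 15-20% replaced). These figures assume that the 20% null refers to all treated subjects and, for the last two ranges, that all drop-out occurs after treatment starts. The thresholds, the total of 24 and the enrolment of 30 are arithmetically sound.

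**What to change.** Put one definition, independent of outcome, in Sections 4.1, 9.2, 11.1 and 11.2.3:

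- Every Phase II subject who starts study treatment counts toward the 14 and the 24, whatever doses are missed.
- A counted subject with no response assessment, for any reason, is a non-responder.
- Only subjects who never start treatment are replaced.
- The CR rate in the evaluable set is reported as a sensitivity analysis.

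Also state in Section 11.1 which population the 20% and the 40% describe.

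The cost is wording in four sections, with no new data or visits and fewer replacements. The reported CR rate may be lower. If the 40% was meant for completers only, keeping 2/14 and 8/24 means accepting power of about 0.60 at 15% drop-out or 0.51 at 20%, against 0.80. The plan should state that loss, or recalculate the design for the all-treated rate it expects.
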